#### 3.7.3 Exploratory Procedural Success

Procedural success will be assessed at 30 days post-implant procedure. All of the following must be present:

- Device success •
- Absence of major device or procedure related serious adverse events (SAEs): Life threatening bleed; major • vascular or cardiac structural complications requiring unplanned reintervention or surgery; Stage 2 or 3 AKI (includes new dialysis); MI or need for PCI/CABG; stroke; severe HF or hypotension requiring IV inotrope, ultrafiltration or mechanical circulatory support; prolonged intubation > 48 hours; any valve-related dysfunction, migration, thrombosis, or other complication requiring surgery or repeat intervention

## 3.7.4 Exploratory Individual Patient Success

Individual patient success will be assessed at 12 months post-device implant. All of the following must be present:

- **Device success** ۲
- Patient returned to pre-procedural setting (i.e., return to prior living arrangement or equivalent)

For Use Only by Page 11 of Affiliates of 18 Lifesciences

Edwards

Title

Edwards

Statistical Analysis Plan for TRISCEND Study (2019-06)

- No-rehospitalizations or re-interventions for the underlying condition (TR, HF)
- Improvement from baseline in symptoms (NYHA class improvement  $\geq 1$  class)
- Improvement from baseline in functional status (6MWD improvement  $\geq$  30 meters) •
- Improvement from baseline in QOL (KCCQ improvement  $\geq$  10 points) •

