8.6. Study Exit Criteria and Procedures

All patients that sign an informed consent document for this study will have the study exit reason documented in the medical record and on the appropriate eCRF. Patients may exit the study for any of the following reasons:

- **Screen Failure:** Patients who are consented to participate in the study, but do not fulfill enrollment criteria.

- **Study Device Attempted but Not Implanted:** Enrolled patient for whom the implant procedure was prematurely aborted will be followed either for 30 days (for only safety evaluations) OR until resolution, stabilization, or is adequate explanation of any implant-related AEs and then exited from the study. Examples include:
 - Procedure attempted (i.e. skin incision to introduce the EVOQUE System) but patient did not receive a study device
- **Study Device Re-intervention/Explant:** Patient who has a surgical re-intervention for study device explant will be followed for 30 days after the re-intervention for safety evaluations only or until resolution of any AEs related to the re-intervention and then exited from the study. Note: a patient who has a percutaneous re-intervention where the study device remains in place will continue to be followed for the duration of the study.
- **Withdrawal**
 - **Patient Withdrawal:** A patient may voluntarily withdraw from the clinical study at any time, without penalty or loss of benefits to which they are otherwise entitled.
 - **Physician Withdrawal:** An Investigator also has the right to withdraw a patient if s/he feels it is in the best interest of the patient to do so.
- **Patient death**
- **Lost to Follow-up**
 - If a patient cannot be reached for a follow-up visit, the Investigator will document contact efforts and/or efforts to obtain hospital records in the appropriate eCRF. If a patient cannot be reached in any way, or misses a visit, the patient will be considered “unable to contact” for that time interval.
 - After 3 documented unsuccessful attempts to make contact, a certified letter will be sent to the patient’s residence. If there is no response after a certified letter is sent, the patient will be classified as “lost to follow-up”.
- **Completion Per Protocol**

Withdrawn patients will not have any study follow-up visits or procedures after the time of study exit. All data collected up until the time of withdrawal, including imaging studies such as echocardiography scans, will be analyzed.

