### 3.7.2 Exploratory Device Success

Device success will be assessed at 30 days, 6 and 12 months, and annually until 5 years post-implant procedure. All of the following must be present:

- Absence of procedural mortality or stroke •
- Proper placement and positioning of the device •
- Freedom from unplanned surgical or interventional procedures related to the device or access procedure •
- Intended safety and performance of the device including: •
  - No evidence of structural failure (e.g., major fracture, malpositioning, frozen prosthetic leaflet) or functional failure (e.g., for hemodynamic performance, the device maintains insufficiency relief without producing TV stenosis)
  - No specific device-related technical failure issues and complications (e.g., para-device complications, device-related pulmonary embolism)
  - TR reduction of at least 1 grade from baseline

Structural and functional failure will be assessed by the echo core lab. Intended safety and performance of the implanted device will be assessed at each visit. If previously identified safety or performance issues resulting in device failures at earlier visits are no longer present via TTE at a later visit (e.g., a previously identified paravalvular leak or frozen prosthetic leaflet is no longer present), a patient may be considered to have device success at the later visit.

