### 6. DATA AND ANALYSIS CONVENTIONS

#### 6.1 General Conventions

For continuous variables, results will be summarized with the number of observations, mean, standard deviation, median, minimum, maximum, and 90% confidence interval (CI) by normal approximation. For categorical variables, results will be summarized with patient count, percentage, and 90% CI by normal approximation, where appropriate.

Survival analysis techniques will be used to analyze time-to-event variables. Patients without events will be censored at their last participation date in the study. For patients who did not have an event but remain in the study, they will be censored at the database extract date. Time to first event curves will be constructed using Kaplan-Meier estimates. Descriptive statistics will be presented at each assessment, including change from baseline to subsequent time point for selected endpoints. For the determination of event rates, the number of patients in the patient population who have had the events or have been followed up to the upper bound of the follow-up visit window will be used as the denominator. Unless otherwise noted, patients with missing data will be excluded from the denominator.

When the sample size is small (e.g., <10 patients), analysis may be performed in the form of listings only.

Quality of life questionnaires will be scored according to algorithms provided by the vendor. The various summary scores produced by the algorithms will be analyzed as continuous variables.

Unless otherwise specified, confidence limits will be two sided, using alpha = 0.05.

Unless otherwise specified, the precise form of each algorithm will be the default of SAS, using the latest release installed at Edwards Lifesciences (Edwards) at the time of analysis.

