#### 6.2 Handling of Missing Data

For AEs with partial onset dates, if the year is not missing, imputation will be performed by finding the earliest possible date on or after the index procedure. If the year is missing, no imputation will be performed.

E	Revision Date: August 1, 2022		Rev		For Use Only by Affiliates of Edwards Lifesciences	Page 13 of 18
Edwards	Title	Statistical Analysis P	lan foi	r TRIS	CEND Study	v (2019-06)

For endpoint-related AEs (such as MAEs) with partial dates, in addition to applying the imputation method above, the sponsor will review the events and related records on a case-by-case basis, and manually verify the imputed dates. All imputations will be documented and filed in the Trial Master File (TMF).

For missing data due to patient withdrawal or lost to follow-up in the analyses of time-dependent endpoints, the patients will be censored on the last participation date as stated above.

Unless otherwise specified, all statistical analyses will be performed using only those patients with available data required for endpoint analysis, and no other missing value imputation will be performed.

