#### 8.7 Patient-centered Exploratory Endpoints

The patient-centered exploratory endpoints (as described in Section 3.7) will be analyzed as categorical variables and counts and percentages in the AT population.

- Exploratory Device Success (30 days and all post-procedural intervals)
- Exploratory Procedural Success (30 days)
- Exploratory Technical Success (at exit from OR/Cath lab)
- Exploratory Individual Patient Success (1 year)

The patient-centered exploratory endpoints (as described in Section 3.7) will be analyzed as categorical variables and counts and percentages in the AT population.

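### Individual Patient Success: the default missing-data rules drop patients who die before the 12-month assessment from the denominator, which raises the reported rate

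*SAP*

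**What the plan says.** SAP 3.7.4 sets the time point and the success rule: "Individual patient success will be assessed at 12 months post-device implant. All of the following must be present". Three components need a value at the 12-month visit compared with baseline: NYHA class, 6-minute walk distance and quality of life ("Improvement from baseline in QOL (KCCQ improvement" of at least 10 points). Another is event-based: "No-rehospitalizations or re-interventions for the underlying condition (TR, HF"). Exploratory Device Success is also a component. Under SAP 3.7.2 it includes "Freedom from unplanned surgical or interventional procedures related to the device or access procedure", and its only mortality criterion concerns procedural death.

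SAP 8.7 lists "Exploratory Individual Patient Success (1 year") and asks for counts and percentages in the As-Treated (AT) population. Neither 3.7.4 nor 8.7 mentions unavailable components, death or study exit.

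The general rules are in SAP 6.1, "Unless otherwise noted, patients with missing data will be excluded from the denominator", and SAP 6.2, "all statistical analyses will be performed using only those patients with available data required for endpoint analysis". SAP 6.2 also rules out further imputation. Protocol 12.3 likewise bases follow-up-visit variables on evaluable patients.

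Under Protocol 8.6 death is a study exit. A patient whose device is surgically explanted "will be followed for 30 days after the re-intervention for safety evaluations only or until resolution" of related adverse events, and then exits.

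**The concern.** A patient who dies at month 4 has no 12-month NYHA class, walk distance or KCCQ score. No exception is noted for this endpoint, so the defaults treat the patient as missing and remove them from the denominator. Yet this is a responder composite in which every component must be met at 12 months, and such a patient cannot meet it. The percentage labelled as AT then describes only patients who survived to be assessed, and each death before the visit raises it.

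The study's stated objectives include guiding future study designs. A success proportion that improves as patients die is a poor input for that. Two programmers could also follow the SAP in good faith and report different rates.

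**Working it through.** **No planned figure to reproduce.** SAP 2.3 gives up to 200 patients with no statistical justification. The documents state no success, death or explant rate for this endpoint. All rates below are assumptions.

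**Step 1: which rule applies.**
- SAP 3.7.4 and 8.7 contain no rule for death or study exit, so the proviso in SAP 6.1 for noted exceptions is not triggered.
- SAP 8.4 has one failure-type value: a walk distance of zero for patients who cannot walk for a medical reason. It does not name death or study exit.
- SAP 6.1 also has an event-rate denominator: patients who had the event, or were followed to the upper end of the visit window (365 + 45 = day 410). If the event is success, patients who leave early without success drop out, which gives the same bias. If the event is a listed failure, a later death with no earlier listed failure is still lost.

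**Step 2: direction.** Let N be the AT patients, D those who die after the procedure and before the assessment, and S the successes. For simplicity, assume no other missing data.
- Deaths counted as not successful: S/N.
- Deaths excluded: S/(N − D).
- Ratio: 1/(1 − D/N). It exceeds 1 whenever D > 0. For D/N of 5%, 10% and 15% it is 1.05, 1.11 and 1.18.

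**Step 3: size.** Write p for the success rate among evaluable patients and d = D/N. The AT rate is p(1 − d) and the excess is p × d.

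| Assumed d | p = 35%: AT rate | Excess (points) | p = 50%: AT rate | Excess (points) |
|---|---|---|---|---|
| 5% | 0.35 × 0.95 = 33.25% | 1.75 | 0.50 × 0.95 = 47.5% | 2.5 |
| 10% | 0.35 × 0.90 = 31.5% | 3.5 | 0.50 × 0.90 = 45.0% | 5.0 |
| 15% | 0.35 × 0.85 = 29.75% | 5.25 | 0.50 × 0.85 = 42.5% | 7.5 |

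In counts, with N = 200 (all implanted), D = 20 and S = 80, exclusion gives 80/180 = 44.4% (90% CI 38.4 to 50.5). Counting deaths as not successful gives 80/200 = 40.0% (34.3 to 45.7). The intervals use the normal approximation that SAP 6.1 names for categorical variables.

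**Step 4: explants, rehospitalisations and re-interventions.** These patients fail an observed component (3.7.4, or 3.7.2 through Device Success), so their outcome can be determined. The SAP has no rule that one failed component settles the composite when others are missing. SAP 8.3 also removes patients from the echocardiographic analysis once they have a tricuspid re-intervention, so the TR-reduction component may be missing too. They may be dropped or kept, depending on the programmer. They are not in the table.

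**The case against.** The best counter-argument is that the SAP never orders the exclusion. Read together, the all-components rule and the AT denominator could lead a programmer to count anyone not shown to meet every component as not successful. That reading is possible. But the all-components rule defines success and does not address unavailable components, whereas SAP 6.1 and 6.2 do address them and apply by default.

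A reader might infer that the same rules clearly remove explanted patients and those rehospitalised for HF. The documents do not support that: one observed failure can be taken as the data needed to classify the patient. For this group the gap is an ambiguity.

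A reader might also infer that every death in the first year is a failure under the endpoint's own list. It is not. Only procedural mortality is listed, and counting death from any cause makes the definition more explicit. The 1-year window is ±45 days, so it opens at day 320, and a patient who dies late in the year may already have been assessed.

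Three further points stand:
- Living patients too ill to walk get a distance of zero under SAP 8.4 and so fail that component.
- All-cause mortality, HF hospitalisation and non-elective re-intervention are reported separately with Kaplan-Meier rates in the AT population (SAP 8.4), so deaths are not hidden.
- The endpoint is exploratory, appears only in the SAP (section 10), and has no test or threshold.

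These limit the stakes but do not correct the percentage.

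**Conclusion.** The point holds for deaths after the procedure and before the 12-month assessment. The stated defaults take these patients out of the Individual Patient Success denominator, and the rate is overstated by the factor 1/(1 − D/N). The direction is certain once the defaults are applied. The size is not, because the documents give no death rate: about 1.8–2.5, 3.5–5.0 or 5.3–7.5 points for assumed deaths of 5%, 10% or 15% and assumed success of 35% to 50% among evaluable patients.

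For patients who leave after an explant, or after rehospitalisation or re-intervention for TR or HF, the SAP is silent, and they may or may not be dropped. The effect is on one exploratory, descriptive estimate. It does not touch the 30-day safety endpoint. The change is worth making because a stated rule biases the figure in a known direction and wording alone removes it.

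**What to change.** Add to SAP 3.7.4 and 8.7:

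> The denominator is the AT population. A patient is counted as not a success, whether or not other components are missing, if any of these holds: (a) death from any cause before the 12-month assessment; (b) before that assessment, an event that the definition does not allow to be reversed, namely procedural stroke, study device explant, an unplanned procedure related to the device or access, or rehospitalisation or re-intervention for TR or HF; (c) failure of any component measured at the 12-month visit. Device findings that have resolved by the 12-month TTE follow the recovery provision in 3.7.2. NYHA, 6MWD or KCCQ values from earlier visits do not count as failures. Patients with no failed component and at least one undeterminable component are reported as missing, with a sensitivity analysis that counts them as failures.

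The time point in (c) and the two sentences after it are needed. A general rule that any failed component counts would conflict with the recovery provision in 3.7.2, and could fail a patient for not having improved at 30 days.

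For Exploratory Device Success, state that explanted patients count as failures at all later visits.

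The cost is SAP wording. Deaths, explants and hospitalisations are already recorded. The downside for the sponsor is a less favourable reported success rate.

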#### **ANALYSIS POPULATIONS** 4.

Analysis will be performed for the Enrolled, As-Treated (AT), and Per-Protocol (PP) populations defined below:

- Enrolled Population: All patients enrolled in the study, defined as patients who sign informed consent and have had the study procedure attempted (attempted defined as skin incision for study device). Enrolled population will be used for the safety analyses.
- As-Treated Population: A subset of the enrolled population who have had the study device implanted at • the exit of procedure room. The AT population will be the analysis population for performance and functional endpoint analysis.
- Per-Protocol Population: A subset of the AT population who had no protocol deviations relating to • inclusion and exclusion criteria for the trial.

#### DEFINITIONS 5.

#### 5.1 Analysis Dates and Days

Reference Start Date and Day 0

The reference start date is defined to be the date of the index procedure. The index procedure is defined as the time the first skin incision for the study device is established. If a patient has multiple procedure forms, information will be presented on the procedure with the first date when the site has indicated that the interventional skin incision for study device is performed. If no form has this indicated, then the procedure information corresponding to the date of the first procedure will be used.

The reference start date is considered to be day 0.

Last Participation Date

The Last Participation Date is defined as the last date the patient was seen (refer to the programming convention for complete details).

Last Participation Day

Last Participation Day = Last Participation Date – Reference Start Date

Note: Last Participation Day is used as censor day for Kaplan-Meier analysis.

	Revision Date: August 1, 2022		Rev		For Use Only by Affiliates of Edwards Lifesciences	Page 12 of 18
Edwards	Title	Statistical Analysis P	lan foi	 TRIS	CEND Study	r (2019-06)

• Study Day

Study Day = Date – Reference Start Date

#### 5.2 Analysis Windows

An assessment is considered scheduled if the assessment is identified by a nominal visit name (e.g., "Discharge," "30 day," and "1 year") regardless of if the actual visit date is within the protocol-defined visit window. An assessment is considered unscheduled if no nominal visit name is identified. Unless specified, any functional endpoints collected from unscheduled assessments should be excluded from analyses.

### 6. DATA AND ANALYSIS CONVENTIONS

#### 6.1 General Conventions

For continuous variables, results will be summarized with the number of observations, mean, standard deviation, median, minimum, maximum, and 90% confidence interval (CI) by normal approximation. For categorical variables, results will be summarized with patient count, percentage, and 90% CI by normal approximation, where appropriate.

Survival analysis techniques will be used to analyze time-to-event variables. Patients without events will be censored at their last participation date in the study. For patients who did not have an event but remain in the study, they will be censored at the database extract date. Time to first event curves will be constructed using Kaplan-Meier estimates. Descriptive statistics will be presented at each assessment, including change from baseline to subsequent time point for selected endpoints. For the determination of event rates, the number of patients in the patient population who have had the events or have been followed up to the upper bound of the follow-up visit window will be used as the denominator. Unless otherwise noted, patients with missing data will be excluded from the denominator.

When the sample size is small (e.g., <10 patients), analysis may be performed in the form of listings only.

Quality of life questionnaires will be scored according to algorithms provided by the vendor. The various summary scores produced by the algorithms will be analyzed as continuous variables.

Unless otherwise specified, confidence limits will be two sided, using alpha = 0.05.

Unless otherwise specified, the precise form of each algorithm will be the default of SAS, using the latest release installed at Edwards Lifesciences (Edwards) at the time of analysis.

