8.13. Post-Procedure Cardiac Rhythm Monitoring

All study patients will have ECGs performed:

- within 24 hours prior to the procedure (Section 8.10.2 “Implantation Procedure”)
- 12-24 hours post procedure (Section 8.14.1 “Post-Procedure Study Procedures/Data Collection”)
- at discharge (Section 8.15 “Discharge Evaluation/Data Collection”)
- as needed per physician discretion (e.g., if new ECG changes are noted).

All study patients will be monitored on telemetry in-hospital for at least 24 hours post-procedure.

All study patients will be monitored by an ambulatory cardiac monitor for at least 2 weeks immediately following discharge (except those with pre-existing or newly implanted functional permanent pacemaker (PPM), implantable cardioverter defibrillator (ICD), cardiac resynchronization therapy (CRT) devices, or implantable cardiac monitor (ICM) with real-time monitoring service).

Use of the Sponsor provided ambulatory cardiac monitoring device is preferred. Investigator may select an alternative commercially available monitoring device, per local routine practice, if deemed medically necessary.

Patients will be treated per institutional standard of care if ECG changes are identified. Newly identified clinically significant ECG changes will be reported as adverse events.

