### 8.1 Safety Endpoint

The safety endpoint of MAEs at 30 days shall be analyzed via the Kaplan-Meier method for the Enrolled and AT populations. In addition, the event rates of individual component of MAEs will also be calculated at 30 days, 6 months, and annually until 5 years post-procedure by the Kaplan-Meier method:

- Cardiovascular mortality •
- Myocardial infarction (MI) •
- Stroke •
- Renal complications requiring unplanned dialysis or renal replacement therapy •
- Severe bleeding (includes fatal, life-threatening, extensive, or major bleeding, as defined by MVARC) •
- Non-elective tricuspid valve re-intervention, percutaneous or surgical •
- Major access site and vascular complications •
- Major cardiac structural complications •
- Device-related pulmonary embolism

The number and percentage of patients with at least one MAE at 30 days will be summarized. The number of MAE at 30 days, 6 months, and annually will be reported as well. Additional analyses of safety endpoints using the PP population will be performed if there is/are a clinically meaningful difference(s) from the enrolled and AT populations.

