### 9.3 Cardiac Monitoring

The counts and percentages of patients who experience newly identified ECG changes, as identified by ambulatory cardiac monitoring, resulting in PPM, ICD, or CRT device implantation will be reported. Two-sided 90% confidence intervals will be constructed around the percentages of patients who experience newly identified ECG changes resulting in PPM, ICD, or CRT device implantation. These analyses will only include patients who undergo ambulatory cardiac monitoring. The reported confidence intervals will be compared to the ranges reported in the literature data.

The count and percentage of patients who have a change in therapy (either new pacemaker for bradycardia or new ICD/new pharmacotherapy for tachycardias) as a result of ECG changes identified by ambulatory cardiac monitoring will be reported. This analysis will only include patients who undergo ambulatory monitoring.

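### SAP 6.1 names only a normal-approximation 90% interval for percentages; when events are few it under-covers and its upper limit is usually too low, and SAP 9.3 is the analysis most exposed

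*SAP*

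**What the plan says.** The rule for percentages is in SAP 6.1: "For categorical variables, results will be summarized with patient count, percentage, and 90% CI by normal approximation, where appropriate". Protocol 12.3 has the same rule. The closing qualifier leaves room for judgement but gives no criterion and no substitute.

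Two other sentences in SAP 6.1 might seem to fill the gap:

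- The small-sample rule: "When the sample size is small (e.g., <10 patients), analysis may be performed in the form of listings only". It depends on the number of patients, not the number of events. Two events among 150 patients would not trigger it.
- The sentence that defers to SAS defaults. It applies only where nothing else is specified, and here the normal approximation is specified.

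Neither document names an exact or score interval for a proportion.

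SAP 9.3 (and Protocol 12.5) then calls for an interval: "Two-sided 90% confidence intervals will be constructed around the percentages of patients who experience newly identified ECG changes" that lead to a pacemaker, ICD or CRT implant. No method is given, so SAP 6.1 governs. On the denominator: "These analyses will only include patients who undergo ambulatory cardiac monitoring". On the use of the result: "The reported confidence intervals will be compared to the ranges reported in the literature data". Protocol 8.13 prescribes ambulatory monitoring for all study patients "except those with pre-existing or newly implanted functional permanent pacemaker (PPM), implantable cardioverter defibrillator (ICD"), and the exemption goes on to CRT devices and to implantable monitors with a real-time service.

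**The concern.** The normal-approximation interval takes its width from the observed proportion. When few events are observed, that width is too small, and with no events it is zero. The interval is also symmetric about the estimate, although the sampling distribution at low rates is skewed. For a safety percentage the expected failure is an upper limit that is too low.

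SAP 9.3 is where this matters most, because its interval is the one the SAP sets against outside figures. Its denominator is below the enrolled number by at least the exempt patients, and devices implanted before discharge do not enter its numerator. Both features make a small count more plausible, though neither establishes one. If the count is small, the comparison with the literature could make the device look safer than the data can show. One stated objective (SAP 2.1) is to guide later study designs, so such a reading could be carried forward.

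**Working it through.** **No plan figure to reproduce.** SAP 2.3 says that no statistical justification was used for the sample size, and no precision target is given. The check is therefore whether the stated 90% level is achieved.

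**Inputs**

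- Level 90%, two-sided, normal approximation: SAP 6.1 and 9.3. z = 1.645.
- Maximum n = 200: SAP 2.3 and Protocol 12.1.
- Number monitored: not given. Assumed 100, 150 and 200.
- True rate: not given. Assumed 1-5%, in steps of 0.05 percentage points (81 rates), with every method evaluated on the same grid.

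**Formulas.** With x events in n and p̂ = x/n, the normal interval is p̂ ± 1.645 × √(p̂(1 − p̂)/n). Actual coverage at true rate p is the sum of the binomial probabilities P(X = x) over every x whose interval contains p.

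**One case in full: n = 200, p = 3%**

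- x = 3: 0.015 ± 1.645 × √(0.015 × 0.985/200) = 0.09% to 2.91%. Misses, upper limit too low.
- x = 4: 0.37% to 3.63%. Covers.
- x = 11: lower limit 0.055 − 1.645 × √(0.055 × 0.945/200) = 2.85%. Covers.
- x = 12: lower limit 0.060 − 1.645 × √(0.060 × 0.940/200) = 3.24%. Misses, lower limit too high.

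Coverage is therefore P(4 ≤ X ≤ 11) = 83.4%. Of the remaining 16.6%, 14.7 points come from x ≤ 3, where the upper limit is too low. Zero events have a probability of only 0.2% here, so the shortfall is not just the zero-event case.

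**Normal interval over rates of 1-5%**

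| n | Mean coverage | Minimum | Misses with upper limit too low | Misses due to zero events |
|---|---|---|---|---|
| 200 | 86.7% | 73.4% | 85% | 13% |
| 150 | 85.6% | 73.5% | 88% | 26% |
| 100 | 82.6% | 63.1% | 92% | 51% |

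At n = 200 the minimum falls at a rate of 1.35%, where zero events account for about a quarter of the misses. At n = 100 it falls at 1%, where zero events (probability 36.6%) account for nearly all of them.

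**Alternatives on the same grid (n = 100-200)**

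- Clopper-Pearson: mean coverage 93.9-95.6%, never below 90%.
- Wilson: mean coverage 90.6-91.3%, minimum 85.7%.

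**What would be printed (90% limits)**

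| Events | Normal | Wilson | Clopper-Pearson |
|---|---|---|---|
| 0/200 | 0 to 0% | 0 to 1.3% | 0 to 1.5% |
| 2/200 | −0.2 to 2.2% | 0.3 to 3.0% | 0.2 to 3.1% |
| 3/200 | 0.1 to 2.9% | 0.6 to 3.7% | 0.4 to 3.8% |
| 5/200 | 0.7 to 4.3% | 1.2 to 5.1% | 1.0 to 5.2% |

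**Where the problem fades.** At rates of 10-20% and n = 200, normal-interval coverage is 87.1-91.2%.

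**The case against.** The strongest reply has three parts.

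First, low rates are assumed. No section gives an expected rate or the number monitored, and n = 100 supposes that half of a full enrolment goes unmonitored. At the one documented figure, n = 200, average coverage is 90 − 86.7 = 3.3 points below nominal. This stands: the size of the effect is conditional, and the n = 100 figures mark the far end of the range.

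Second, the qualifier in SAP 6.1 means that nobody is obliged to print a 0-0% interval. This also stands, but with no criterion and no substitute the method would have to be chosen after the counts are seen.

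Third, this is a descriptive, single-arm feasibility study. Counts accompany the intervals, and the literature comparison has no threshold. This stands too, and limits the consequence to interpretation.

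A reader might go further and infer that the 30-day MAE result is compromised. The documents do not support that. SAP 8.1 says "The safety endpoint of MAEs at 30 days shall be analyzed via the Kaplan-Meier method for the Enrolled and AT populations" and asks for no interval. If one were shown, SAP 6.1 already settles the level: 90% for a percentage, and otherwise "Unless otherwise specified, confidence limits will be two sided, using alpha = 0.05". A composite rate of 10-20% would in any case be little affected by the normal approximation.

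A reader might also want the monitoring exemption repaired here. Leaving out devices implanted before discharge concerns what SAP 9.3 estimates, and no choice of interval changes that.

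**Conclusion.** The point holds as a minor one. The only interval that the plan names for percentages falls short of its 90% level when events are few, and in most misses the upper limit is below the true rate. On average the shortfall is 3.3, 4.4 and 7.4 points (90 minus 86.7, 85.6 and 82.6) at n = 200, 150 and 100, and it is larger at particular rates. This rests on assumed true rates of 1-5% and an assumed number monitored of 100-200. If the SAP 9.3 rate proves to be 10% or more with n near 200, little changes. No test, threshold or stopping rule uses these intervals, so what is at stake is how the SAP 9.3 comparison is read.

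**What to change.** In SAP 6.1, replace the normal approximation for percentages with the two-sided 90% Clopper-Pearson interval, and name the same method in SAP 9.3. Clopper-Pearson suits a safety percentage because its coverage does not fall below 90%. Wilson is acceptable if average coverage near 90% is enough. Either way, choose one before the data are reviewed. Add a line to SAP section 10, because Protocol 12.3 names the normal approximation and that section now lists only the patient-centered exploratory endpoints.

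The cost is a few lines of SAP text and slightly wider intervals. For 5 of 200 the width goes from 4.32 − 0.68 = 3.6 points to 5.18 − 0.99 = 4.2 with Clopper-Pearson, or 5.05 − 1.22 = 3.8 with Wilson. No additional data or patients are needed.
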